1. SYNOPSIS

Study Title	Operational evaluation of Mass Screening and Treatment using ultrasensitive rapid detection tests to reduce P. falciparum malaria incidence and prevalence in a malaria elimination program in Eastern Kayin State, Myanmar.	
Internal ref. no.	MAL 17011	
Study Design	Stepped wedge intervention	
Study Participants	Populations of villages with high P. falciparum incidence located in Eastern Kayin State, Myanmar.	
Planned Sample Size	60 villages (group 1) 60 villages (group 2)	
Planned Study Period	3 years	
	Objectives	Outcome Measures
Primary	To measure the impact of URDT-based MSAT on P. falciparum incidence at village-level (group 1 & 2)	Adjusted incidence rate ratio before/after MSAT
Secondary	1) To measure the impact of MSAT on prevalence of P. falciparum infection in malaria hotspots (group 1)	1) Prevalence of P. falciparum infection measured in the village by URDT and by reference method
	2) To measure the impact of reactive MSAT on incidence of seasonal malaria peaks / outbreaks (group 2)	2) Change in the incidence dynamics over the transmission season
	3) Feasibility of MSAT as a programmatic tool and as a reactive strategy (group 1 and 2)	3) Coverage of village population with intervention
	4) % of infections treated compared to infections detected by reference method (group 1 only)	4) % of P. falciparum positive samples by reference method which were positive by URDT and treated; % of P. falciparum negative samples by reference method which were positive by URDT and treated

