Figure 3: Average *P. falciparum* and *P. vivax* incidence in hotspots before and after MDA, centered on date of MDA. A marked decrease in *P. falciparum* incidence after MDA can be observed, in spite of an increase in incidence around 15 months after MDA. This increase is related to 5 hotspots (out of 52 followed up to M18) showing an incidence above 50 case/1000 for 1 month during the second year after MDA. This increase did not persist further.

In this project, we aim at an operational research deployment of URDT-based MSAT in the METF elimination program. This intervention will be tested in two types of setting, which correspond to two arms in this study. In group 1, MSAT will be used in a programmatic setting in order to decrease the reservoir of asymptomatic carriers in high incidence villages (following the same principles and objective as previously deployed MDA interventions). In group 2, we take advantage of the lighter framework of MSAT to use it as a reactive intervention in order to respond to malaria outbreaks in low to intermediate incidence villages. The MSAT intervention will be preceded with community-level consent and community engagement (CE) activities. MSAT will be conducted over a period of approximately 1 week in each hamlet, village or group of villages, and will consist in administering a *P. falciparum* URDT to all individuals agreeing to participate. A limited subgroup (expected 5-25%) will be found positive and receive supervised treatment over 3 days for the standard regimen (DP to cure asexual stage infection + single low-dose primaquine to destroy gametocytes). After this intervention, the incidence of clinical falciparum episodes will be monitored by the village MP. In group 1, a comparison of the prevalence at baseline and 12 months after MSAT intervention will be performed through a second URDT survey, in addition to which both baseline and 12-month surveys will include the collection of a 50 μ L capillary blood sample for reference detection in the laboratory.

The intervention will be evaluated primarily on its ability to reduce yearly cumulative incidence of clinical falciparum malaria compared to year before intervention. Additional evaluations of the impact of MSAT will include: in group 1, comparison of asymptomatic infection prevalence; and in group 2, modifications of the shape of the incidence curve following intervention.

Potential risks and benefits for participants

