5. STUDY DESIGN

Stepped-wedge open-label, non-randomized, cluster intervention.

This study will be performed in clusters (hamlet (isolated group of household, village, or group of village). The intervention will be conducted in two types of clusters, both corresponding to locations where an excess of case was detected.

Group 1: Sustained high incidence clusters, characterized by a yearly cumulative incidence >84 cases/1000/year

Villages in group 1 will be attributed an intervention a given year based on the cumulative incidence over the previous 12 months (METF stratification January, including the last 2 transmission seasons). The order of intervention will be decided based on logistic constraints and highest incidence.

Group 2: Focal transmission clusters, corresponding to locations where an epidemic alert has been signalled and confirmed (see definition of thresholds).

*Villages in group 2 will be attributed an intervention based on *P. falciparum* incidence in the previous 4 weeks. In near-0 transmission area, an intervention will be conducted in each likely source location of transmission of a locally acquired case. In the other areas (METF1+METF2), the intervention will be triggered when the incidence is above the pre-defined epidemic threshold.*

In each cluster, all inhabitants will be invited to undergo an URDT test to identify their infection status, and will receive the appropriate treatment according to their characteristics. Information on village inhabitants absent during the MSAT activities will be obtained from village population lists provided by the village headman and from household member declarations. During the URDT screening, all individuals will receive a unique identifying number that will be used to record demographic data in the MSAT paper logbook and to label URDT and reference sample.

Before and after MSAT intervention, incidence of clinical malaria episodes will be recorded at the MP (1 or several) serving the cluster receiving the intervention. No individual data will be collected to link clinical case participation, infection status and incidence of clinical episodes.

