6. PARTICIPANT IDENTIFICATION AND RECRUITMENT

6.1. Study villages selection

The study village selection is based on the definition of three main strata of *P. falciparum* incidence corresponding to different probabilities of rapid elimination. Based on 2017 data, the townships of Myawaddy, Hlaingbwe and Kawkareik have almost interrupted *P. falciparum* transmission (95% of villages with 0 incidence), while heterogeneity persists in Hpapun township with diverse transmission and incidence profiles.

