6.1.1. Group 1: sustained high incidence villages

Villages classified as high incidence, low probability of elimination (*P. falciparum* cumulative incidence >84 cases/1000/year, in spite of >1 year of functioning malaria post) will be eligible to be included in group 1. Villages in this group will be addressed by MSAT waves of 10-15 villages.

Villages will be included in a given wave based on accessibility to the team and proximity from each other, as well as requirements for the program impact. Wave 1 will include 5 villages and be conducted during first semester 2018, after which a maximum of two waves will be conducted per semester.

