9. STATISTICS AND ANALYSIS

9.1. Description of Statistical Methods

Coverage of intervention: the coverage of the intervention will be defined as the proportion of individuals screened by URDT divided by the total number of individuals present in the village during the next

Before/after MSAT yearly cumulative incidence and 95% Poisson confidence intervals will be calculated using:

- Numerator: the total number of *P. falciparum* cases reported during the weeks with an MP report.
- Denominator: the village population size measured during the MSAT * number of weeks with an MP report during the year (number of weeks of MP activity).

Analysis including the entire follow-up available for malaria posts will be conducted in order to provide adjusted estimates on the

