9.2.1. Sample size for stepped-wedge comparison of incidence decrease following MSAT

MSAT will be implemented in 60 villages with high 1-year cumulative incidence of *P. falciparum* clinical cases in 6 waves of 10 villages (1 wave per semester). Assuming a baseline cumulative incidence of 250 cases/1000/year, a population of 190 inhabitants per village with a 0.49 coefficient of variation in cluster size and an intra-cluster correlation coefficient of 0.12, the expected detectable difference between villages with and without intervention is <25 cases/1000/year for alpha=0.01 & beta=0.9.

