9.3. Analysis of Outcome Measures

Primary outcome: stepped-wedge comparison of incidence.

The incidence comparison will be conducted over a 2-year series of weekly incidence data, corresponding to 12 months before and 12 months after MSAT intervention. A generalized additive multilevel mixed model will be used to adjust for location, season, and temporal trend due to MP activity using uni-(seasonality, duration of MP activity in the village) or bivariate (latitude and longitude) splines, including random intercept and slopes at village level. MSAT intervention will be included in the model as a 0-1 variable. The incidence rate ratio obtain for this variable will quantify the average decrease in incidence after MSAT campaign compared to before.

Secondary outcome: before-after comparison of prevalence

For each village, the fractional change in prevalence before MSAT and 12 months after will be calculated and compared to 0% change. This change will be compared to the fractional change observed after MDA.

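### As readable, the primary model in 9.3 has no calendar-time effect, so part of an unusual year shared by villages can enter the MSAT rate ratio, in either direction

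*Combined protocol and SAP*

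**What the plan says.** Section 5 calls the design "Stepped-wedge open-label, non-randomized, cluster intervention". Under Section 3, MSAT is "evaluated primarily on its ability to reduce yearly cumulative incidence of clinical falciparum malaria compared to year before intervention". The Synopsis applies the primary objective to both groups: "incidence at village-level (group 1 & 2".

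Section 9.3 models weekly incidence from 12 months before to 12 months after MSAT in each village. It adjusts for "temporal trend due to MP activity using uni-(seasonality, duration of MP activity in the village) or bivariate (latitude and longitude) splines" and adds village random intercepts and slopes; the slope variable is not named. MSAT is a 0/1 term whose rate ratio is read as after against before.

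Section 9.1 adds: "Analysis including the entire follow-up available for malaria posts will be conducted". That sentence stops before any adjustment variable can be read. This is lost text, not a fault of the plan, but it leaves some doubt about the full adjustment set.

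Two rollouts appear. Section 9.2.1 treats 60 villages "in 6 waves of 10 villages (1 wave per semester". Section 6.1.1 starts with 5 villages in the first semester of 2018, "after which a maximum of two waves will be conducted per semester", in waves of 10 to 15.

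On geography, Section 6.1 reports of 2017, first for Myawaddy, Hlaingbwe and Kawkareik: "95% of villages with 0 incidence), while heterogeneity persists in Hpapun township with diverse transmission and incidence profiles".

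**The concern.** A seasonal curve that repeats each year cannot represent one good or bad year. MP duration runs parallel to calendar time within a village, but opening dates differ, so a spline on duration common to all villages follows a shared calendar shock only in part. Random village slopes on time would take up only a linear part. What remains can be carried by the MSAT term, because MSAT also switches from 0 to 1 on calendar dates that many villages share.

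The outcome is a comparison with the year before, so a shared difference between years competes directly with the MSAT effect. Most group 1 villages plausibly lie in Hpapun and could share such a year, although its varied profiles mean that the shock need not be uniform. The order of rollout is not randomised. The more villages are treated in the same few months, the less the untreated villages can separate the year from the intervention.

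**Working it through.** **1. The plan's own figure.** Inputs from 9.2.1: 60 villages in 6 steps of 10, 190 inhabitants, 250/1000/year, intra-cluster correlation 0.12, alpha 0.01, power 0.9. The Hussey-Hughes variance with period effects (I = 60 clusters, T = 7 periods) is

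Var = I·σ²(σ² + Tτ²) / [(IU − W)σ² + (U² + ITU − TW − IV)τ²].

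- σ² = 0.88 × 0.25 × 0.75 / 190 = 0.000868; τ² = 0.12 × 0.1875 = 0.0225.
- U = 210, W = 9,100, V = 910.
- Numerator: 60 × 0.000868 × (0.000868 + 7 × 0.0225) = 0.00825.
- Denominator: 3,500 × 0.000868 + 14,000 × 0.0225 = 318.0.
- Standard error = √(0.00825/318.0) = 0.00509; times 3.857 (2.576 + 1.282) this is 0.0196, or 19.6/1000/year.

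The coefficient of variation of 0.49 changes this very little. Without period effects the result is about 12.7. Both agree with the stated limit of under 25, so that figure does not show which form was used. Reading each period as a half-year risk of 0.125 gives 29.4 to 31.4 with period effects.

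**2. How unevenly one year falls before and after MSAT.** Assume waves at mid-semester from early 2018, 12-month windows, a flat rate otherwise, and 2018 at 1.5 times the usual rate. Crude ratio = (1 + 0.5 × share of after-time in 2018) / (1 + 0.5 × share of before-time in 2018).

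- 6 × 10: before 10 × (0.25 + 0.75 + 0.75 + 0.25)/60 = 0.333; after 10 × (0.75 + 0.25)/60 = 0.167; ratio 1.083/1.167 = 0.93.
- 5, 20, 20, 15: before 35/60 = 0.583; after 8.75/60 = 0.146; ratio 1.073/1.292 = 0.83.
- 5, 25, 30: before 42.5/60 = 0.708; after 10/60 = 0.167; ratio 1.083/1.354 = 0.80.

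If 2019 is the high year, 5, 25, 30 gives 1.354/1.0625 = 1.27, the opposite direction. These are unadjusted ratios, before the model absorbs anything.

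**3. What remains after the 9.3 adjustment.** A Poisson model was fitted with village effects, a cyclic season, a spline on MP duration and the 0/1 MSAT term, with true IRR 1. Assumptions that the documents do not fix: one shared year at 0.6 or 1.5 times the usual rate, MP opening dates with SD 0.25 to 1.0 years, and 4 to 8 spline degrees of freedom.

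| Villages per semester | Fitted IRR, no calendar term | Type I error, half-year shocks |
|---|---|---|
| 10 × 6 (9.2.1) | about 0.94–1.06 | 4–8% and 7–9% in two sets of runs |
| 5, 20, 20, 15 | about 0.93–1.08 | not run |
| 5, 25, 30 | about 0.86–1.18 | 16–50% and 11–33% |

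- Both later schedules fit 6.1.1: 20 = 10 + 10, 25 = 10 + 15, 30 = 15 + 15. After the first 5, the other 55 villages need at least two semesters at 30 each, so three semesters is the minimum.
- Under 6 × 10 the median shift is 1.7%. For a milder year (0.8 or 1.25 times) the worst case is 0.97–1.03. With no shocks, type I error in the first set of runs was 5–8%. With shocks, the SD of log IRR is 3–28% larger than when 3-month effects are fitted.
- Village-specific slopes leave worst cases of 0.93–1.06 (6 × 10) and 0.84–1.20 (5, 25, 30).
- A smooth log-linear trend is largely absorbed by the MP-duration spline. The leak comes from non-linear departures.

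**4. With a calendar term.** For 6 × 10 and 5, 25, 30, 95% of settings lie in 0.97–1.03 with 3-month effects (type I error 4–9%) and in 0.99–1.01 with a date spline of 6 knots per year. A second set of runs gave about 0.98–1.02 with either term.

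**5. Full MP series.** Without a calendar term the worst cases widen to 0.90–1.11 (6 × 10) and 0.72–1.42 (5, 25, 30). With a date spline they are 0.99–1.01.

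**The case against.** - *Seasonality may already mean a smooth over calendar date, or the lost end of the 9.1 sentence may name such a term.* Either would nearly close the point. Neither is stated, so the claim holds only for the readable text. A reader might infer that the sponsor has certainly left calendar time out; the documents do not support that.
- *The effect is small under the only schedule tied to the primary comparison.* This stands for 6 × 10. One wave per semester within 6.1.1 sizes (5, 10, 15, 15, 15) also kept type I error at 3–8%. Reaching 5, 25, 30 needs the maximum of two waves in both later semesters. A schedule that ends on a wave of 5 would fall outside 6.1.1 and is no evidence here. A faster rollout is not far-fetched, however: six waves at one per semester already fill the 3 years in the Synopsis before the last villages have their 12 months of follow-up.
- *The figures rest on assumptions.* This stands. The documents give no shock size, and 9.3 names no standard error. The type I figures in the table use village-robust errors for the first set of runs. A further set for 6 × 10 gave about 9–12% with robust and 13–22% with model-based errors.
- *Date and MP duration overlap.* Date is opening date plus duration, so within a village their linear parts cannot be separated. This is a caveat on reading those curves. The MSAT term remains estimable.
- A reader might also infer that 9.2.1 assumed period effects which 9.3 then dropped. The stated figure fits both forms, so no contradiction is shown.

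**Conclusion.** The point holds as a gap in the readable primary model that should be fixed, with moderate confidence. It is not a claim that the trial fails or that the model favours MSAT: the shift can go either way.

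Its size depends on the rollout. Section 9.2.1 aims at a difference under 25 on 250, that is, under 10%. Under 6 × 10 an assumed 0.6 or 1.5 times year moves the ratio by up to about 6%, type I error stays near nominal, and the main loss is precision. Under 5, 20, 20, 15 the shift is up to about 8%. Under 5, 25, 30 it reaches about 14 to 18%, larger than the difference the trial is sized for, with clearly inflated type I error.

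All these figures are illustrations under assumed shocks, opening dates and spline flexibility. They are not properties of the plan. They model group 1. Adding 60 group 2 villages at an assumed 30/1000/year gave similar worst cases (0.93–1.06 and 0.85–1.20).

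**What to change.** Add to the 9.3 model a calendar-time effect common to all villages, either 3-month period effects or a smooth of date with about 6 knots per year. Keep the cyclic season and MP-duration splines. If seasonality already means a smooth over date, say so. Do not interpret the linear date and MP-duration trends separately.

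State two limits: a common term does not remove area-specific shocks, which matter because 7.4 aims to treat an area's villages together, and it does not remove regression to the mean in villages chosen for high recent incidence.

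Use the full MP series only with the calendar term. Separately, reconcile the wave schedule (6.1.1 with 9.2.1) and the analysis window (Section 4 and 9.1 with 9.3).

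The cost is one model term on data already held. With 3-month effects and no shocks, the standard error of log IRR goes from 0.0577 to 0.0580 for 6 × 10 (0.5%) and from 0.0586 to 0.0614 for 5, 25, 30 (4.8%). The second set of runs, with either term, gave a rise of about 0 to 3%. The larger gap in the design formula (12.7 against 19.6) overstates the cost, because it compares with a model that has no time terms at all, whereas 9.3 already spends precision on season and MP duration.

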7.4. Randomisation, blinding and code-breaking

No randomization will be conducted. Villages with sustained high incidence will be assessed every 6 months and prioritized based on accessibility/feasibility. As much as possible, all villages from a given area will be addressed at the same time in order to maximize impact of interventions.

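### Group 1 MSAT dates are set by area, but the primary model and sample size stop at village level, so the rate-ratio interval will be too narrow if neighbouring villages share changes in incidence over time

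*Combined protocol and SAP*

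**What the plan says.** Timing in group 1 follows geography. Section 6.1.1 states: "Villages will be included in a given wave based on accessibility to the team and proximity from each other". Section 7.4, which also states that nothing is randomised, adds: "As much as possible, all villages from a given area will be addressed at the same time in order to maximize impact of interventions". Section 5 allows the treated unit to be larger than a village: "This study will be performed in clusters (hamlet (isolated group of household, village, or group of village".

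The analysis stays at village level. The primary model in 9.3 is a generalised additive mixed model on weekly incidence, over a window "corresponding to 12 months before and 12 months after MSAT intervention". It has splines for season and for duration of malaria post activity, plus "bivariate (latitude and longitude) splines, including random intercept and slopes at village level". The treatment term is simple: "MSAT intervention will be included in the model as a 0-1 variable". No area or wave effect, area-by-time term or area-clustered variance is described.

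The sample size uses the same unit. Section 9.2.1 states "MSAT will be implemented in 60 villages with high 1-year cumulative incidence", arranged "in 6 waves of 10 villages (1 wave per semester". It assumes 250 cases per 1000 per year, 190 inhabitants per village, a size CV of 0.49 and an intra-cluster correlation of 0.12. It concludes that a difference below 25 per 1000 per year is detectable at alpha 0.01 with 0.9 power (printed as beta).

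**The concern.** The latitude/longitude spline removes lasting differences in level between places. It has no time dimension, so it cannot remove a bad or quiet season that hits one area. The season spline is not described as varying by area. Section 9.3 does not say which covariate the village slopes belong to, but as village-level effects they would ordinarily be independent from one village to the next.

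When all villages of an area switch on one date, a fluctuation they share falls on the same side of that date for all of them. The 0-1 term then takes it up as if several villages had each supplied separate evidence. With no randomisation, the primary claim rests on this model, so a false standard error goes straight into the interval and p-value of the primary result. The detectable difference in 9.2.1 is optimistic for the same reason.

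**Working it through.** **1. Reproducing the stated bound.** I used the Hussey-Hughes variance for N clusters and T periods:

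Var = Nσ²(σ² + Tτ²) / [(NU − W)σ² + (U² + NTU − TW − NV)τ²].

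Inputs from 9.2.1: N = 60, six steps of 10 (T = 7), incidence 0.25, 190 per village, ICC 0.12. I assumed a two-sided test, since sidedness is not stated, and read the printed beta as power.

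- Total variance: 0.25 × 0.75 = 0.1875.
- τ² = 0.12 × 0.1875 = 0.0225.
- σ² = 0.88 × 0.1875 / 190 = 0.000868.
- U = 210, W = 9100, V = 910, so the denominator is 3500σ² + 14000τ² = 318.04.
- Numerator: 60 × 0.000868 × (0.000868 + 0.1575) = 0.008252.
- Var = 0.00002595 and SE = 0.00509.
- Detectable difference: (2.576 + 1.282) × 0.00509 = 0.0196, or **19.6 per 1000 per year**.

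Multiplying σ² by 1 + 0.49² gives 21.9. Poisson counts (σ² = 0.25/190) give 24.2. All are below 25, so the bound reproduces with independent villages and a full year of risk per step. With half a year per step (σ² = 0.25/95) it would be 34.1.

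**2. Adding an area-by-period effect.** The documents give no such variance, so I assumed 5% of τ²: 0.05 × 0.0225 = 0.001125. That is an SD of 0.034, or about 34 per 1000 per year on a baseline of 250. The remaining τ² is 0.021375.

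If the shocks are independent between periods, the formula applies to area means.

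- *One area of 10 per wave:* N = 6, σ² = 0.000868/10 + 0.001125 = 0.001212, τ² = 0.0021375. Var = 6 × 0.001212 × (0.001212 + 7 × 0.0021375) / (35 × 0.001212 + 140 × 0.0021375) = 0.000344. SE = 0.01855, detectable difference 71.6.
- *Two areas of 5 per wave:* N = 12, σ² = 0.000868/5 + 0.001125 = 0.001299, τ² = 0.004275. Var = 12 × 0.001299 × (0.001299 + 7 × 0.004275) / (140 × 0.001299 + 560 × 0.004275) = 0.000189. SE = 0.01374, detectable difference 53.0.

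For autocorrelation of 0.7 between periods I solved the same design by generalised least squares.

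| Areas | Detectable difference per 1000 per year (autocorrelation 0.7 to independent) | Power for 25 per 1000 per year |
|---|---|---|
| No area effect | 19.6 | above 0.9 |
| 5 villages | 40.0 to 53.0 | 0.44 to 0.22 |
| 10 villages | 51.9 to 71.6 | 0.24 to 0.11 |

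**3. Effect on the 9.3 interval.** This is a linear approximation on the log rate with village intercepts and slopes, season, post duration, a fixed location surface and the 0-1 MSAT term. The model variance is (D′V₀⁻¹D)⁻¹. The true variance puts V, which is V₀ plus the shared area shock, in the middle of the corresponding sandwich. The model SE is 0.059 throughout. Assumed shocks have SD 0.1 to 0.4 and autocorrelation 0.9 to 0.7 from period to period.

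| Areas | Shock SD | True SE | Ratio to model SE | Coverage of nominal 95% |
|---|---|---|---|---|
| any | 0 | 0.059 | 1.00 | 95% |
| 5 | 0.1 | 0.064 to 0.068 | 1.07 to 1.14 | 93 to 91% |
| 5 | 0.2 | 0.076 to 0.089 | 1.27 to 1.50 | 88 to 81% |
| 5 | 0.4 | 0.111 to 0.145 | 1.86 to 2.44 | 71 to 58% |
| 10 | 0.1 | 0.068 to 0.076 | 1.14 to 1.27 | 91 to 88% |
| 10 | 0.2 | 0.089 to 0.111 | 1.49 to 1.87 | 81 to 71% |
| 10 | 0.4 | 0.144 to 0.197 | 2.43 to 3.30 | 58 to 45% |

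Giving each village its own autocorrelated shock does not cure this. The ratios are then 1.05 to 1.57 (areas of 5) and 1.12 to 2.09 (areas of 10).

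**The case against.** The strongest reply is that everything depends on an area-by-time variance the documents never give. The signs they do offer are mixed. The location-specific seasonal peaks in section 3 concern *P. vivax*. The rise in falciparum about 15 months after MDA came from 5 of 52 hotspots, and the protocol does not say whether these were neighbours. With no shared variation the planned interval is right. This reply stands against any flat statement that the interval is wrong. It does not make zero a safe assumption. Section 6.1.2.2 plans for local transmission episodes at cluster level, and 7.4 treats areas together for impact, which suggests that neighbours share transmission.

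A reader might go further and infer that the 60 villages amount to about six independent blocks. A simulation of that case (six areas of ten villages, shared SD 0.2 and 0.3, weekly autocorrelation 0.95) gave false-positive rates of 30.5% and 41.5% at nominal 5%, and 5.0% without shared variation. The documents do not support this as the expected case. They never equate a wave with one area, the grouping in 7.4 is only where feasible, and wave membership also depends on access, programme needs and incidence. With areas of 5 and SD 0.1 to 0.2, the coverage above implies false-positive rates of about 7 to 19%. With areas of 2 or 3 villages the ratios are 1.03 to 1.89.

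A reader might also extend the point to the whole primary objective. Group 2 dates come from surveillance triggers, not an area schedule, so the argument does not carry over.

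Finally, the worst figure above, 71.6, is 29% of the 250 baseline (71.6/250), so a halving of incidence would still be detectable. That limits the harm to the design, not the harm to the interval. The last sentence of 9.1 on adjusted estimates is cut off in the available text, so further detail may exist there.

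**Conclusion.** The point holds for group 1, conditionally. Dates are grouped by area, while the model and sample size recognise only villages. Any positive area-by-time variation makes the MSAT interval too narrow, and only zero shared variation makes it correct. The size cannot be derived from the documents. Over the assumed range it runs from slight (1.07) to severe (3.3) on the standard error. A 5% area-by-period share roughly doubles to nearly quadruples the detectable difference. The stated bound of 25 is not an arithmetic error: it follows from its village-level inputs, with a full year of risk per step, and silently assumes no such correlation.

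**What to change.** **Section 9.3.** Before analysis, define the areas treated together and record each village's area and date. Add an area-by-calendar-time random effect, or a location-by-time smooth, to the primary model. Report the MSAT interval with variance clustered by area and a small-sample correction. The correction matters: in a small simulation (150 runs per setting, no village slopes), uncorrected area-robust intervals with six areas covered only about 0.83 to 0.89. Per-area log rate ratios with a t interval can serve as a sensitivity analysis at most, since they give up the between-wave comparison. Permuting dates between areas is not advised, because the dates were not randomised and depend partly on incidence.

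**Section 9.2.1.** State that the bound of 25 assumes no area-by-time correlation, and restate the detectable difference over a stated range of it. Reconcile the step structure at the same time: 6.1.1 has a first wave of 5, then waves of 10 to 15 with up to two per semester, while 9.2.1 has six waves of 10, one per semester.

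**Cost.** Analysis and sample-size text only, with no change to field work. The price is a wider interval and a less favourable stated detectable difference. If the shared variation proves negligible, little precision is lost.

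### As most naturally read, the primary model has no term for village surges that last weeks, so the interval for the MSAT rate ratio may be too narrow, by an amount the documents do not fix

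*Combined protocol and SAP*

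**What the plan says.** Section 9.3 sets the data: "The incidence comparison will be conducted over a 2-year series of weekly incidence data, corresponding to 12 months before and 12 months after MSAT intervention". That is about 104 weekly counts per village. The method follows: "A generalized additive multilevel mixed model will be used to adjust for location, season, and temporal trend due to MP activity". Season and MP duration enter as univariate splines and location as a bivariate spline, with "splines, including random intercept and slopes at village level. MSAT intervention will be included in the model as a 0-1 variable". The MSAT coefficient is the primary result: "The incidence rate ratio obtain for this variable will quantify the average decrease in incidence after MSAT campaign compared to before".

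Section 9.3 names no distribution, no variables for the random slopes, no serial correlation, no village-by-period effect and no cluster-robust variance. Poisson appears only in section 9.1, for descriptive intervals: "Before/after MSAT yearly cumulative incidence and 95% Poisson confidence intervals will be calculated using". The last sentence of 9.1, on adjusted estimates from the whole MP follow-up, breaks off in the available text. It can be neither relied on nor held against the plan.

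The protocol itself expects short village surges:
- The Figure 3 legend (section 3) reports "5 hotspots (out of 52 followed up to M18) showing an incidence above 50 case/1000 for 1 month".
- Section 4 makes the length and height of the seasonal peak a secondary measure in group 2.
- Section 5 brings group 2 clusters in on incidence over the preceding four weeks.
- Section 6.1.2.2 generates outbreak alarms by village or cluster.

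**The concern.** The MSAT rate ratio is largely a before/after contrast within villages. Its precision therefore depends on how incidence moves over time inside a village. A random intercept removes a village's level, and a slope on time or MP activity removes steady drift. Neither absorbs a rise that lasts some weeks and then fades, and a shared seasonal spline cannot follow peaks peculiar to one village. If such rises occur, neighbouring weeks carry overlapping information, and a model that counts them as separate evidence reports too small a standard error.

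At stake are the width of the primary confidence interval and the false-positive rate of its test. Section 9.2.1 plans at alpha 0.01, where a modest understatement of the standard error multiplies the error rate.

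**Working it through.** **1. The plan's own figure.** Section 9.2.1 states a detectable difference below 25/1000/year, with 60 villages "in 6 waves of 10 villages (1 wave per semester"), 190 inhabitants, size CV 0.49, ICC 0.12, alpha 0.01 and power 0.9 (the plan writes beta = 0.9). The Hussey-Hughes variance was used with I = 60, T = 7 periods and annual risk 0.25 in each period.
- Between-village variance: 0.12 × 0.1875 = 0.0225.
- Within-village variance of a period mean: 0.88 × 0.1875 / 190 = 0.000868.
- Design sums: U = 210, W = 9,100, V = 910.
- Variance: 60 × 0.000868 × (0.000868 + 7 × 0.0225) / (3,500 × 0.000868 + 14,000 × 0.0225) = 0.0000259, so SE = 0.00509.
- Detectable difference: (2.576 + 1.282) × 0.00509 = 0.0196, or 19.6/1000/year. With the size divided by 1 + 0.49² it is 21.9.

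The stated figure is reproduced on these terms. The calculation uses one ICC, constant over time, so it does not allow for village-specific fluctuation either.

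**2. Closed-form check.** Take one village of 190 with weekly mean μ, and a log-rate that fluctuates with SD s and week-to-week correlation ρ. Neither s nor ρ is in the documents; both are assumed. For the difference between two adjacent 52-week totals, the variance relative to Poisson is approximately

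V = 1 + μ s² F, with F ≈ (1 + ρ)/(1 − ρ) − 3ρ/[52(1 − ρ)²].

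F is 5.22 at ρ = 0.7 and 13.8 at ρ = 0.9. The Poisson standard error is understated by √V. With a simple over-dispersion scale the factor is √[V/(1 + μ s²)].

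At 250/1000/year, μ = 190 × 0.25 / 52 = 0.913:
- s = 0.3, ρ = 0.7: V = 1 + 0.913 × 0.09 × 5.22 = 1.43, so 1.20 fold; over-dispersed √(1.43/1.08) = 1.15.
- s = 0.8, ρ = 0.9: V = 1 + 0.913 × 0.64 × 13.8 = 9.07, so 3.0 fold; over-dispersed √(9.07/1.58) = 2.4.

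The second case is the extreme corner, and the formula ignores the village slope, which absorbs some slow drift. At 84/1000/year (μ = 0.307) the same corner gives √3.71 = 1.93, and at 20/1000/year (μ = 0.073) √1.65 = 1.28.

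**3. Simulation with no MSAT effect.** 60 villages by 104 weeks, 6 waves, seasonality, and village variation in level and trend, with autoregressive weekly noise as above. Models were fitted by penalised quasi-likelihood with a village intercept and time slope and no spatial spline, 120 to 200 runs per cell. Entries are true SD of the log rate ratio divided by mean model SE, with 95% interval coverage.

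| s, ρ | Poisson | Negative binomial | Poisson + random MSAT effect |
|---|---|---|---|
| none | 0.97 (95.0%) | 0.96 (95.0%) | 1.00 (95.0%) |
| 0.5, 0 | 1.21 (89.5%) | 0.97 (95.0%) | 1.07 (92.5%) |
| 0.5, 0.7 | 1.78 (73.5%) | 1.42 (80.0%) | 1.04 (92.5%) |
| 0.5, 0.85 | 2.06 (63.5%) | 1.57 (76.7%) | 1.06 (94.2%) |
| 0.8, 0.7 | 2.40 (55.8%) | 1.44 (80.0%) | not run |
| 0.8, 0.85 | 3.20 (48.3%) | 1.89 (71.7%) | 1.10 (93.3%) |

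Over-dispersion deals with independent weekly noise (row 2) but not with correlated noise. In the correlated rows, type I error at nominal 1% is 17 to 41% (Poisson) and 8 to 17% (negative binomial). With a random MSAT effect it is 1 to 3%.

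**4. Documented surges alone.** A share p = 5/52 of villages has one burst of b = 0.050 × 190 = 9.5 cases on top of m cases a year. Then V = 1 + p(1 − p)b²/(m + pb), where p(1 − p)b² = 7.84 and pb = 0.91.
- 250/1000/year, m = 47.5: V = 1.16, SE understated 1.08 fold.
- 84/1000/year, m = 15.96: V = 1.46, 1.21 fold.
- 20/1000/year, m = 3.8: V = 2.66, 1.63 fold.

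**The case against.** The strongest reply is that the slopes are plural and undefined. If one of them is a village-level slope on MSAT, coverage in the correlated settings returns to roughly 93 to 94% and most of the problem goes. That stands. The trend reading is more natural, because MSAT is introduced in its own sentence as a single 0-1 term, but it remains an inference. Leaving the choice open is not harmless: the mean Poisson model SE is about 0.055 without the MSAT slope and 0.084 to 0.138 with it.

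A reader might infer that the interval is two to three times too narrow and that the 1% test errs 17 to 41% of the time. The documents do not support that as a finding. Those figures need both a Poisson family, which 9.3 does not name, and assumed values of s and ρ.

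Nor do the Figure 3 surges calibrate those values. They occurred around 15 months after MDA, beyond the 12-month window of 9.3. The 20/1000/year mean in section 9.2.3 belongs to the first year after MDA, so it is not their baseline. At 250/1000/year, a month at 50/1000 is only 50/(250/12) = 2.4 times the average month. On the other side, step 4 counts one kind of extreme burst in five villages and no smaller fluctuation, so it is not an upper bound.

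Finally, the simulation uses group 1 planning values, whereas the primary objective covers both groups.

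**Conclusion.** The concern holds conditionally. As written, 9.3 contains no stated term that carries village-specific fluctuation over weeks. On the natural reading of the slopes, the primary interval is too narrow whenever such fluctuation exists, and over-dispersion alone does not repair it. The direction is secure; the size is not. Across the assumed range at 250/1000/year, the understatement is about 1.2 to 3 fold under Poisson and about 1.1 to 2 fold with over-dispersion, where only the extreme corner of the slope-free formula goes higher. It shrinks at lower incidence under the same proportional noise. The documented surges alone give about 1.1 fold at 250/1000/year, rising at lower incidence because a burst of fixed size then weighs more. If the slopes already include MSAT, little remains beyond saying so.

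**What to change.** In section 9.3:
- Name the count distribution and the variables that carry random slopes.
- Include a village-level random MSAT effect.
- Take the primary interval for the MSAT rate ratio from a whole-village bootstrap, or from a village-clustered variance with a small-sample correction. In a separate null simulation (400 data sets per setting, assumed weekly correlation 0.8 to 0.9 in the correlated settings), clustered variance held the nominal 5% test at 5 to 7%, against 31 to 52% for the model-based error.
- Treat a village-by-month or autoregressive term as an optional addition.

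Beforehand, estimate residual autocorrelation from the incidence series already held; section 9.2.3 takes its ICC from them. This would replace the assumed s and ρ.

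The cost is SAP wording and a few lines of code. The downside is a wider interval if autocorrelation is present. In the simulated model at alpha 0.01 and power 0.9, the detectable reduction is 1 − exp(−3.857 × SE). It moves from about 19% (SE 0.0548; 48/1000/year of 250) with no serial correlation to between 28% (SE 0.0863; 71/1000/year) and 44% (SE 0.1519; 111/1000/year). If autocorrelation is negligible, little is lost: the mean model SE goes from 0.0548 to 0.0595.
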